## **6.3 Participant numbering, treatment assignment, randomization**

### **6.3.1 Participant numbering**

Each participant is identified in the study by a Participant Number (Participant No.) that is assigned when the participant is first enrolled for screening and is retained as the primary identifier unless the participant is re-screened. The Participant identifier consists of the Center Number (Center No.), (as assigned by Novartis to the investigative site) with a sequential Participant No. suffixed to it, so that each patient's participation is numbered uniquely across the entire database. Upon signing the informed consent form, the site will use the electronic data capture system to assign the participant the next sequential Participant No.

Once assigned, the Participant No. must not be reused for any other participant and the Participant No. for that individual must not be changed unless the participant is re-screened. If the patient fails to be enrolled or start treatment for any reason, the reason will be entered into the appropriate eCRF page. Re-screening is allowed once for participants that were initially screen failures for any reason. All eligibility criteria must be re-checked and met prior to enrollment of the participant into the study. A new Participant No. should be assigned for all re-screened patients.

### **6.3.2 Treatment assignment, randomization**

Not applicable.

## **6.4 Treatment blinding**

Not applicable.

## 6.5 Dose Modification

Dose escalation is not applicable.

For participants who do not tolerate the protocol-specified dosing schedule, dose modifications consisting in dose interruptions are either recommended or mandated in order to allow participants to continue the study treatment.

Dose modifications for HMA will be done according to local practice and US package insert. Dose modifications for MBG453 (sabatolimab) will be done according to ASCO guidelines about management of immune-related AEs including hematological AEs ([Brahmer et al 2018](#)). Additionally, the guidance indicated in [Table 6-3](#) below provides instructions for infusion reaction, immune-related adverse events not covered by ASCO guidelines and a general guideline for non-hematologic non-immune-related toxicities that are clinically significant per investigator judgement and possibly attributable to the investigational drug. This general guideline will not apply in case of non-hematologic non-immune-related toxicities that are attributable to HMA or MDS and its complications.

General guidelines are to follow local practice, US package insert, and ASCO guidelines for HMAs. Further guidance is provided below.

Deviations to mandatory dose interruptions, reductions and/or permanent discontinuations are not allowed.

- **Dose modifications for MBG453 (sabatolimab)** (See [Table 6-3](#) and refer to [Brahmer et al 2018](#))

Administration of MBG453 (sabatolimab) may be delayed due to toxicities. A scheduled dose may be delayed within a cycle by up to 14 days. If a dose cannot be administered within the planned window within the cycle then the dose should be skipped. Next scheduled dosing may resume once the adverse event has resolved to  $\leq$  Grade 1 or baseline and the cycle will be shifted accordingly. Dose reductions for MBG453 (sabatolimab) are not allowed; however, longer intervals for administration (Q8W instead of Q4W) are permitted in some clinical situations, as described in [Table 6-3](#).

Overall, for adverse events of potential immune-related etiology (irAE) that do not recover to  $\leq$  Grade 1 or baseline at a dose of immunosuppression of  $\leq$  10 mg/day prednisone or equivalent (or as indicated in [section 6.5.1](#)) within 12 weeks after initiation of immunosuppressive therapy, MBG453 (sabatolimab) must be permanently discontinued.

- **Dose modifications for HMA**

If azacitidine or decitabine or INQOVI (oral decitabine) treatment is deemed by the investigator to possibly have contributed to an observed adverse event, the dose or schedule of hypomethylating agent treatment may be modified within a cycle and/or for subsequent cycles or temporary/permanent interruptions of HMA treatment may be decided by the investigator according to local practice and/or the US package insert guiding azacitidine or decitabine or INQOVI (oral decitabine) use.

- **Permanent discontinuation of MBG453 (sabatolimab) and HMA**

If the study treatment is interrupted for toxicities and the start of the subsequent study treatment cycle is delayed for more than 56 consecutive days (i.e. 2 planned consecutive cycles of study

treatment for both, HMA and MBG453 (sabatolimab) the participant should be discontinued from study treatment.

- **Permanent discontinuation of only one component MBG453 (sabatolimab) or HMA**

If **one component only** of the study treatment (HMA OR MBG453 (sabatolimab)) is discontinued for toxicities, then the treatment may continue with the other component of study treatment alone (MBG453 (sabatolimab) or HMA alone) as long as the participant benefits per investigator's judgement.

All dose changes must be recorded on the appropriate CRF.

Criteria for re-initiation of study drug MBG453 (sabatolimab) for adverse drug reactions

**Table 6-3 Criteria for re-initiation of study drug MBG453 (sabatolimab) for adverse drug reactions**

Worst Toxicity CTCAE v5.0 Grade	Dose Modifications
Infusion Reaction*	
Grade 1	Decrease infusion rate until recovery
Grade 2	Stop infusion Before restarting – pre-medicate according to local institutional guidelines. Restart infusion at 50% of previous rate under continuous observation. Ensure that there is a minimum observation period of 1 hour prior to restarting the infusion(s) If the AE recurs at the reinitiated slow rate of infusion, and despite adequate pre-medication, then discontinue treatment
Grade 3 or 4	Discontinue MBG453 (sabatolimab)  For toxicities thought to be immune-related and not covered in the ASCO Guidelines for the management of immune-related adverse events in participants treated with immune checkpoint inhibitor therapy
Grade 1	No change. Continue MBG453 (sabatolimab) at the same dose (800 mg) and schedule (Q4W)
Grade 2 or Grade 3 $\leq$ 7 days	Delay MBG453 (sabatolimab) until toxicity resolved to $\leq$ Grade 1 or baseline. Then resume at the same dose (800 mg) and schedule (Q4W)
Grade 3 lasting $>$ 7 days but $<$ 21 days	Delay MBG453 (sabatolimab) until toxicity resolved to $\leq$ Grade 1 or baseline. Then resume at the same dose (800 mg) but with a longer treatment interval (Q8W). Return to the initial treatment interval (Q4W) may be possible but only after discussion and agreement with Novartis Medical Lead
Grade 3 lasting $\geq$ 21 days Or Grade 4	Discontinue MBG453 (sabatolimab)
General guideline for non-hematologic, non-immune-related toxicities that are clinically significant** and at least possibly attributable to the investigational drug.	
This guideline does not apply for toxicities attributable to HMA (decitabine or INQOVI (oral decitabine) or azacitidine) or the underlying MDS including its complications.	

Grade 1	No change. Continue MBG453 (sabatolimab) at the same dose (800 mg) and schedule (Q4W)
Grade 2 or Grade 3 $\leq$ 7 days	Delay MBG453 (sabatolimab) until toxicity resolved to $\leq$ Grade 1 or baseline. Then resume at the same dose (800 mg) and schedule (Q4W)
Grade 3 >7 days	Delay MBG453 (sabatolimab) until toxicity resolved to $\leq$ Grade 1 or baseline. Then resume at the same dose (800 mg) but with a longer treatment interval (Q8W). Return to the initial treatment interval (Q4W) may be possible but only after discussion and agreement with Novartis Medical Lead
Grade 4	Discontinue MBG453 (sabatolimab)
All dose modifications should be based on the available information and worst preceding toxicity.	
* Infusion related reaction or allergic reaction/anaphylaxis. See section 6.2.1 for instructions regarding prophylaxis.	
** Per investigator judgement.	

### 6.5.1 Follow-up for toxicities

Patients whose treatment is interrupted or permanently discontinued due to an AE or clinically significant laboratory value, must be followed-up at least once a week (or more frequently if required by institutional practices, or if clinically indicated) for 4 weeks, and subsequently at approximately 4-week intervals, until resolution or stabilization of the event, whichever comes first. Appropriate clinical experts should be consulted as deemed necessary.

In addition to the instructions provided in this section, please refer to Section 16.2 (Appendix 2) for further guidance on liver events, laboratory trigger definitions and follow-up requirements. For guidance on renal alert criteria, actions and events follow up, please refer to Section 16.3 (Appendix 3).

All patients must be followed up for AEs for 30 days following the last dose of azacitidine or decitabine or INQOVI (oral decitabine), or 150 days following the last dose of MBG453 (sabatolimab), whichever is later.

### Immune – related AEs

The emergence of Immune-Related AE (irAE) may be anticipated based on general experience in clinical studies with similar class of compounds that block the negative immune regulators.

An irAE is any clinically significant AE affecting any organ that is associated with study drug exposure, is consistent with an immune-mediated mechanism, and where alternative explanations have been investigated and ruled out or are considered unlikely. Serologic, histologic and immunological assessments should be performed as deemed appropriate by the Investigator, to verify the immune related nature of the AE. An empiric trial of corticosteroids may also contribute to understanding the etiology of a potential irAE. All patients with signs or symptoms of irAEs should be monitored and managed following the ASCO Guidelines for the

management of immune-related adverse events in participants treated with immune checkpoint inhibitor therapy.

In case of a suspected irAE, the relevant immunological assessments (e.g. rheumatoid factor, anti-DNA Ab, etc.) should be performed. In case of a toxicity suspected to be a cytokine release syndrome, the assessments outlined in [Table 8-1](#) must be performed.

### **Tumor lysis syndrome**

Tumor lysis syndrome (TLS) is a clinical entity frequently observed in hematological malignancies resulting from massive tumor cells lysis. It is characterized by a constellation of metabolic abnormalities caused by the massive and abrupt release of cellular components (including nucleic acids, proteins, and electrolytes) into the systemic circulation after the rapid lysis of malignant cells ([Coiffier et al 2008](#)). TLS is not frequent in MDS and no cases of TLS has been reported in the ongoing CPDR001X2105 for MDS participants receiving MBG453 (sabatolimab) in combination with decitabine.

During this study, participants should be closely monitored (including relevant laboratory tests) for signs and symptoms of TLS before initiation and during a treatment cycle. To minimize risk of TLS, participants with elevated uric acid or high tumor burden should receive allopurinol, or an alternative prophylaxis, prior to study treatment. Events should be managed according to local guidelines.

Before initiation of a treatment cycle and during a treatment cycle, the following measures should be followed:

- Before initiation of a treatment cycle:
  - Prophylactic allopurinol, or a non-allopurinol alternative (e.g., febuxostat), and increased oral/ IV hydration prior to treatment should be given in participants with elevated uric acid or high tumor burden
  - Prompt supportive care in case of acute TLS (IV fluids and treatment with rasburicase as clinically indicated, when uric acid continues to rise despite allopurinol/febuxostat and fluids)
- During a treatment cycle:
  - Frequent monitoring of the following laboratory tests (per assessment cycle and as clinically indicated): potassium, phosphorus, calcium, creatinine, and uric acid
  - Encourage oral hydration

Based on laboratory and clinical TLS criteria (modified from [Cairo and Bishop 2004](#)), the following measures for TLS should be also followed:

### **Laboratory tumor lysis syndrome**

- Defined as two or more of the following values within 3 days before or in the days following initiation of a treatment cycle:
  - Uric acid  $\geq 8$  mg/dL or 25% increase from baseline
  - Potassium  $\geq 6$  mEq/L or 25% increase from baseline

- Phosphorus  $\geq 6.5$  mg/dL (children) or  $\geq 4.5$  mg/dL (adults) or 25% increase from baseline
- Calcium  $\leq 7$  mg/dL or 25% decrease from baseline
- Regimen:
  - If none or one of the laboratory values above is abnormal, continue to manage with allopurinol or a non-allopurinol alternative (e.g., febuxostat) and oral fluids. If uric acid remains elevated, consider IV fluids, treatment with rasburicase, and hospital monitoring.
  - Laboratory TLS should be managed with IV fluids, laboratory blood tests every 6 to 8 hours and inpatient care. Cardiac monitoring and treatment with rasburicase should be considered if uric acid remains elevated.

### Clinical tumor lysis syndrome

- Defined as the presence of laboratory TLS and  $\geq 1$  of the following criteria that cannot be explained by other causes:
  - Serum creatinine  $\geq 1.5$  times the upper limit of the age-adjusted normal range
  - Symptomatic hypocalcemia
  - Cardiac arrhythmia
  - Regimen: Clinical TLS should be managed with IV fluids, laboratory blood tests every 6 to 8 hours, cardiac monitoring, and treatment with rasburicase/allopurinol/febuxostat and inpatient care (consider intensive care unit (ICU)).

Patients who have been treated for TLS with favorable outcome (defined as return to within 10% of baseline value or within limit of normal of relevant laboratory parameters) may re-start study treatment upon discussion between the sponsor and the investigator.

#### 6.5.1.1 Follow up on potential drug-induced liver injury (DILI) cases

Guidelines for follow-up on potential DILI cases are described in [Table 6-4](#) and [Table 6-5](#).

**Table 6-4 Follow-up of abnormal liver chemistry results**

ALT	TBL	Liver Symptoms	Action
ALT increase without bilirubin increase:			
If normal at baseline: ALT $>3$ x	Normal		- No change to study treatment - Measure ALT, AST, ALP, GGT, TBL, INR, albumin and CK in 48- 72 hours (GLDH is recommended as well) - Follow-up for symptoms
If elevated at baseline: ALT $>2$ x baseline or $>200$ U/L (whichever occurs first)	For participants with Gilbert's syndrome: No change in baseline TBL	None	
If normal at baseline: ALT $>5$ x ULN for more than two weeks	Normal For participants with	None	- Interrupt investigational drug

If elevated at baseline: ALT >3 x baseline or >300 U/L (whichever occurs first) for more than two weeks	Gilbert's syndrome: No change in baseline TBL		
 
- Measure ALT, AST, ALP, GGT, TBL, INR, albumin and CK in 48- 72 hours (GLDH is recommended as well).
 
- Follow-up for symptoms.
 
- Initiate close monitoring and workup for competing etiologies.
 
- Investigational drug can be restarted only if another etiology is identified and liver enzymes return to baseline.
 

If normal at baseline: ALT >8 x	Normal	None	
ALT increase with bilirubin increase:			
If normal at baseline: ALT >3 x	TBL >2 x ULN (or INR >1.5)  For participants with Gilbert's syndrome: Doubling of direct bilirubin	None	
If elevated at baseline: ALT >2 x baseline or >200 U/L (whichever occurs first)			
If normal at baseline: ALT >3 x ULN	Normal or elevated	Severe fatigue, nausea, vomiting, right upper quadrant pain	
If elevated at baseline: ALT >2 x baseline or >200 U/L (whichever occurs first)			

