Study drug discontinuation	Point/time when participant permanently stops taking study drug for any reason; may or may not also be the point/time of premature participant withdrawal.
Study treatment	Any drug administered to the study participants as part of the required study procedures; includes investigational drug (s), control(s) or non-investigational medicinal product(s)
Study treatment discontinuation	When the participant permanently stops taking study treatment prior to the defined study treatment completion date

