## 6 Treatment

### 6.1 Study treatment

In this study, the “study treatment” refers to the combination of study drugs: MBG453 (sabatolimab) plus hypomethylating agent (IV/SC/Oral).

The term “investigational drug” refers to the Novartis study drug, MBG453 (sabatolimab). The choice of the HMA (as described in the following sections) will be selected by the investigator as per local standard of care (SOC). After study enrollment and investigator choice for HMA is decided [whether azacitidine (IV or SC) or decitabine (IV or oral)], type of HMA and mode of administration must not be changed during the study course. In case of emergency clinical care during the study course, it will be allowed for patients switching from oral to IV decitabine during inpatient as per investigator decision. Switching from IV to oral decitabine during emergency clinical care requires following the label to complete the IV cycle to reach steady state of decitabine levels.

All doses prescribed, dispensed to the participant and all dose changes during the study including the reason must be recorded on the appropriate electronic case report form (eCRF) page.

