**Table 16-2 Follow up requirements for liver laboratory triggers with liver symptoms**

Criteria	Actions required	Follow-up monitoring
Potential Hy's Law case a	Discontinue the study treatment immediately Hospitalize, if clinically appropriate Establish causality Record the AE and contributing factors (e.g. conmeds, med hx, lab) in the appropriate CRF	ALT, AST, TBL, Alb, PT/INR, ALP and GGT until resolution c (frequency at investigator discretion)

Criteria	Actions required	Follow-up monitoring
ALT or AST		
>8 × ULN	
Discontinue the study treatment immediately
 
Hospitalize if clinically appropriate
 
Establish causality
 
Record the AE and contributing factors (e.g. comeds, med hx, lab) in the appropriate CRF
	ALT, AST, TBL, Alb, PT/INR, ALP and GGT until resolution c (frequency at investigator discretion)
>3 × ULN and INR >1.5	
Discontinue the study treatment immediately
 
Hospitalize, if clinically appropriate
 
Establish causality
 
Record the AE and contributing factors (e.g. comeds, med hx, lab) in the appropriate CRF
	ALT, AST, TBL, Alb, PT/INR, ALP and GGT until resolution c (frequency at investigator discretion)
>5 to ≤8 × ULN	
Repeat LFT within 48 hours
 
If elevation persists, continue follow-up monitoring
 
If elevation persists for more than 2 weeks, discontinue the study drug
 
Establish causality
 
Record the AE and contributing factors (e.g. comeds, med hx, lab) in the appropriate CRF
	ALT, AST, TBL, Alb, PT/INR, ALP and GGT until resolution c (frequency at investigator discretion)
>3 × ULN accompanied by symptoms b	
Discontinue the study treatment immediately
 
Hospitalize if clinically appropriate
 
Establish causality
 
Record the AE and contributing factors (e.g. comeds, med hx, lab) in the appropriate CRF
	ALT, AST, TBL, Alb, PT/INR, ALP and GGT until resolution c (frequency at investigator discretion)

>3 to $\leq$ 5 $\times$ ULN (patient is asymptomatic)	Repeat LFT within the next week  If elevation is confirmed, initiate close observation of the patient	Investigator discretion  Monitor LFT within 1 to 4 weeks
---	---	--

Criteria	Actions required	Follow-up monitoring
ALP (isolated)		

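### Protocol Tables 6-4 and 16-2 conflict on ALT rises: sabatolimab interrupted with a conditional restart in one, permanent discontinuation in the other, and neither table is said to govern

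*Protocol*

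**What the plan says.** Section 6.5.1.1 of the protocol sends sites to Table 6-4 for raised ALT. For ALT above 5 x ULN for more than two weeks, with normal bilirubin and no symptoms, the action is "Interrupt investigational drug", followed by repeat tests, a work-up and this line: "Investigational drug can be restarted only if another etiology is identified and liver enzymes return to baseline". Section 6.1 defines the investigational drug as sabatolimab alone.

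Table 16-2 in Appendix 2 covers the same laboratory patterns. For ALT or AST above 5 and up to 8 x ULN it says: "If elevation persists for more than 2 weeks, discontinue the study drug". For a potential Hy's Law case, for ALT or AST above 8 x ULN, for above 3 x ULN with INR above 1.5, and for above 3 x ULN with symptoms, it says: "Discontinue the study treatment immediately". Section 6.1 defines study treatment as sabatolimab plus the hypomethylating agent (HMA). Table 16-2 gives no restart rule.

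The glossary defines study drug discontinuation as "Point/time when participant permanently stops taking study drug for any reason" and study treatment discontinuation as "When the participant permanently stops taking study treatment prior to the defined study treatment completion date". Both are permanent.

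Section 6.5.1 tells sites to use Appendix 2 in addition to its own instructions and does not rank them. Section 6.5 forbids deviations from mandatory interruptions, reductions and permanent discontinuations.

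**The concern.** A site that restarts sabatolimab under Table 6-4 has departed from Table 16-2, and nothing in the protocol tells it which table to follow. Two sites can therefore manage the same liver signal differently, each with a written instruction in hand. The signal is not remote: Section 4.2 reports hepatitis with a Grade 3 ALT increase as the one dose-limiting toxicity in the decitabine combination.

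There is also a reporting consequence. Safety is the primary objective. Protocol Section 12.5.2.2 and SAP Section 2.8.1 summarise adverse events leading to discontinuation separately from those leading to dose adjustment or interruption. Which summary a liver event enters depends partly on the table the site followed, not only on what happened to the participant.

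**Working it through.** No sample-size or power figure is involved, so the check is a side-by-side reading. It takes a participant with normal baseline ALT.

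| Pattern | Table 6-4 | Table 16-2 | Result |
|---|---|---|---|
| ALT >5 to 8 x ULN, more than two weeks, bilirubin normal, no symptoms | Interrupt sabatolimab, conditional restart (printed beside the row) | Discontinue study drug, no restart rule | Firm conflict on permanence |
| ALT >8 x ULN, bilirubin normal, no symptoms | No action text beside the row as extracted | Discontinue study treatment at once | Conflict if the action cell is merged |
| ALT >3 x ULN, bilirubin >2 x ULN, alkaline phosphatase not >2 x ULN (potential Hy's Law) | As above | As above | As above |
| ALT >3 x ULN, INR >1.5 | As above | As above | As above |
| ALT >3 x ULN with listed symptoms | As above | As above | As above |
| ALT >3 to 5 x ULN, bilirubin normal, no symptoms | No change, re-test in 48 to 72 hours | Repeat within a week, observe | No conflict on treatment |

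Five of six patterns therefore conflict on action: one on the printed text, and four if the Table 6-4 action is read as one cell covering the rows beneath it.

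**Drug scope.** In the four conditional rows Table 6-4 would interrupt sabatolimab, while Table 16-2 stops sabatolimab and the HMA. In the firm row Table 16-2 says *study drug*, so the component meant is unclear and no scope conflict can be asserted. Scope differs in at most four rows.

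**Elevated baseline.** Inclusion criterion 6 admits ALT up to 3 x ULN. Table 6-4 has thresholds relative to baseline; Table 16-2 has none. Two illustrations assume a ULN of 35 to 55 U/L, which the documents do not give.

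- Baseline 2.8 x ULN, rising to 3.2 x ULN with nausea. The Table 6-4 trigger is 2 x 2.8 = 5.6 x ULN or 200 U/L. The value is 3.2 x 35 = 112 to 3.2 x 55 = 176 U/L, so it is not triggered. Table 16-2 discontinues study treatment.
- Baseline 1.2 x ULN, rising to 4 x ULN for three weeks, bilirubin normal, no symptoms. The Table 6-4 trigger is 3 x 1.2 = 3.6 x ULN (126 to 198 U/L, reached before 300 U/L), so sabatolimab is interrupted. Table 16-2 only repeats the tests and observes.

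**Size.** The documents give no rate of ALT above 3 or 5 x ULN for this combination. The nearest figure is one hepatitis dose-limiting toxicity in 81 participants on the decitabine combination, within the first two cycles: 1/81 = 1.2%, and 39 x 1/81 = 0.5 participant. There was none in 16 on azacitidine. This covers two cycles of a 12-month window and one definition of event, so it does not estimate the number affected. One reclassified participant moves a reported rate by 1/39 = 2.6 percentage points.

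**The case against.** A reader might infer that the tables give opposite instructions in all five situations, Hy's Law included, on both permanence and drug scope. The documents do not support that. Both tables stop sabatolimab at first, so *conflicting* is the right word. Four rows depend on reading blank cells in a damaged table as one merged cell, which is likely but cannot be confirmed from the text. Table 6-4 also never says to continue the HMA; Section 6.5 leaves HMA changes to the investigator under local practice and the US package insert. All of this stands and limits the claim.

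A reader might also size the symptomatic row from the nausea and fatigue rates in Table 1-3. Those are background symptom rates in a mixed AML and MDS group. The trigger also needs ALT above 3 x ULN, and Table 6-4 requires the fatigue to be severe.

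The strongest argument is that restart in Table 6-4 is permissive, so a site that never restarts breaches neither table, and the ban on deviations in Section 6.5 points the same way. But then the restart line would have no use for these triggers at normal baseline ALT, and nothing says so. Nor is Table 16-2 always the stricter one, as the second baseline illustration shows. The words *with liver symptoms* in the title of Table 16-2 do not remove the overlap either, because the table has asymptomatic rows and a separate symptom row.

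On the analysis, the SAP tests no hypothesis and already lists every adverse event with the action taken. Both routes are therefore recoverable, though not shown together.

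**Conclusion.** The conflict holds. For ALT above 5 and up to 8 x ULN lasting more than two weeks it rests on printed text: a reversible interruption against a permanent stop, with both tables in force. For four further triggers, including potential Hy's Law cases, it holds on the assumption that the Table 6-4 action cell extends to the rows below, and there drug scope differs too. The missing elevated-baseline rule in Table 16-2 is a separate mismatch that does not need that assumption.

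The number of participants affected cannot be derived from the documents. No view is taken here on which action is clinically right. The effect on the analysis is limited to how liver events are divided between two descriptive summaries.

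**What to change.** Reconcile Tables 6-4 and 16-2 into one ALT action table with, for each trigger, one action, one restart rule or an explicit statement that there is none, one drug scope and one elevated-baseline rule. State in Section 6.5.1 which text governs. The clinical content is for the clinical team. The cost is amendment wording and a letter to sites.

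Recruitment halted on 30-Sep-2022, and SAP Addendum 02 of 07-FEB-2025 is recorded as written after database lock. The wording change may therefore reach few or no treated participants; the documents do not say whether any remain on treatment. Two steps remain feasible. Disclose the conflict in the clinical study report, and add one listing that shows all liver-triggered interruptions and discontinuations together, by component (sabatolimab or HMA), with baseline ALT and any restart. The listing draws on adverse-event, dosing and laboratory data the SAP already uses, so the cost is one output.
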